**Table 3 Qualitative Data Analysis Protocol**

**Phase 1: Coding** – We will rely on our preliminary work to inform data coding and categorization. We will begin with a coding frame based on prior research and the theoretical framework. Drs. [name], [name], and [name] will take part in analyzing the triangulated data (i.e., the Facebook discussions, photos, and interviews), including discussing and agreeing on the utterance meanings of each code. Once the final list of codes is complete and agreement on codes is met, each qualitative committee member will code separately and meet to discuss interpretations. The coding frame will be modified throughout

analysis, and the committee will review data as they become available. As a way to guide the thematic analysis process, codes emerging from the data will be labeled by at least two members of this committee and discussed at weekly team meetings. Inter-relator reliability (i.e., a Kappa statistic) will be computed via the Dedoose qualitative coding software. When Kappa is .80, we will divide the data and code individually.

**Phase 2: Pattern Identification and Thematic Analysis** – We will build on Phase 1 by reducing the codes until we can make meaning of the data and identify patterns. This reduction process will consist of grouping the codes into smaller themes, or constructs. We will create a cognitive map of the schema for each dataset (control and intervention). All codes will be further reduced and condensed until we reach a consensus on overarching themes that we feel tell the best story of the data and relate to our research questions.

**Phase 3: Trustworthiness** – Along with data triangulation (which is also used to increase trustworthiness of qualitative data analysis), the qualitative data analysis committee will utilize 1) co-coding, 2) peer debriefing with weekly research team meetings, and 3) a strong audit trail linked in a database.

## VII. Potential Risks

**Potential Risks:** Hospice family caregivers will incur minimal risk by participating in the study. Potential risks could include frustration or anxiety with malfunctioning or technically deficient equipment. Some individuals entering the study might not know how to use Facebook, which may cause some anxiety or frustration. Participants may feel nervous about sharing photos on Facebook and engaging with other hospice family caregivers via the private group. They may also feel uncomfortable discussing their caregiving experiences, as well as their bereavement experiences on this platform. As in most studies, despite efforts to protect confidentiality, potential exists for a privacy breach that could cause distress or embarrassment. All paper forms and computerized data will be stored in secure environments to minimize this possibility. Finally, the potential for frustration exists in that study personnel will have an initial phone meeting (orientation) at the beginning of the study as well as communicate with them by phone at the point they become bereaved. We will continue to minimize these risks by being considerate as we contact family by phone. We also assure participants, both verbally and in writing that they may withdraw from the study at any time. Finally, hospice staff will not release names of any potential participants to the research team without first obtaining consent that the research staff can contact them.

The Facebook platform presents special considerations of risk and privacy. The consent form will make these issues known, and the protocol will require research staff to review participants' privacy settings. We recommend the strictest settings. We will tell potential participants that, if they join the study, their name will be added to a "closed secret" Facebook page, giving them access to other hospice family caregivers of persons living with dementia (PLWD) enrolled in the study. Although the research team controls membership in this group, which is not available

to the general public, participants will be advised to protect their personal information and privacy with their individual privacy settings. Members of the Facebook group may contact one another through the Facebook website. However, the research team will not share participants' personal contact information. To participate in the study, participants must join Facebook and have an account. They will be advised to read the Facebook privacy policy and set their Facebook privacy settings with the tightest controls. Our research staff will walk participants through the privacy settings to assist in understanding their meaning. However, participants will decide on their Facebook privacy settings. They will be told that the settings of other group members might affect the privacy of what they share. We also will inform participants of Facebook's policy that it owns all materials placed on the Facebook website, and will advise them to read the policy when posting photos. Should participants feature non-consented individuals in their photos, they will be asked to obtain verbal consent from these individuals before posting the photo in the group. All photos of non-consented individuals will be blurred and de-identified. We will inform participants that, as members of the secret Facebook group, we will encourage them to discuss experiences, share caregiving advice, and access questions and concerns regarding similar issues with others enrolled in the study. Each week, the research staff will provide a new information posting and discussion prompt. We will tell participants that nothing is required of them and that they may log onto the site and read and respond (or not respond) to the discussion as they choose. Our research team will supply discussion information and review all comments and responses to determine members' needs and the helpfulness of the Facebook page. Participants will be given a Rules of Conduct document outlining the ethical conduct expected of the Facebook participants. These rules proscribe giving medical advice to other caregivers or being critical of them. If a participant breaks the rules, the research staff can speak privately with them and, if necessary, after consultation with the Principal Investigators (Drs. [name] and [name]) and research team, revoke their access to the page. The need for this never occurred in our pilot studies. While the Facebook group will not be physically monitored 24/7, all study staff will receive alerts (via Facebook) indicating when and what participant's post. A designated monitoring schedule will be set-up and the Facebook group (and alerts) will be monitored by an actual research staff person between the hours of 7amCST and 10pmCST. Any potential breaches of this code of conduct will be addressed, immediately, the following day. This protocol will be communicated to all participants. This Facebook group does not replace hospice services. Neither the research staff nor any member of the Facebook group will provide mental health services such as counseling. If the research staff becomes concerned about a caregiver's mental well-being, they will contact the hospice social worker to assure the safety of the caregiver and others.

**Protection against Risk:** Caregiver confidentiality and comfort with the technology are protected, for caregivers must agree to participate in the study's Facebook page on their own account. Training staff to understand their role in recruiting participants, as well as preventing a breach of their confidentiality will address this concern. All paper forms and recordings will be kept in locked cabinets in locked offices within a locked suite. All computerized data will be stored on password-protected and encrypted computers and networks. Only study personnel with a specific need to use data will be granted permission to access it. Finally, all patient/family information taken from the home or hospice office will be identified not with names but with an arbitrary identification code. Hospice family caregivers will participate in recorded interviews,

and all recordings will be transcribed and stripped of identifying information. All research data that leave the hospice office will be maintained in a locked file cabinet and secure computer in the PI's office. If written consent is required, the research staff will collect all hard copies of consent forms and hand deliver them to the PI during supervision visits.

### **VIII. Anticipated Benefits**

The proposed project has the potential to improve hospice services by improving hospice support of caregivers from active caregiving and into bereavement. This project's social media platform (Facebook) connects caregivers with other caregivers in a privately moderated group, fostering an environment in which they can obtain additional information and social support that improves both active caregiving and bereavement experiences.

### **IX. Compensation**

Subjects will be compensated \$100 total. One payment of \$50 will be made via a check at the transition period, and the second \$50 payment after completion of their exit interview. During study wind down, all participants will receive their final payment on or around the time of their final survey. Meaning, if participants are on day 90 of 150 and they complete day 90 as their final survey, investigators will initiate final payment. All participants will receive the total amount of their compensation (\$100) at the completion of their final survey, regardless of whether they have entered the bereavement phase.

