### **V. Number of Subjects**

1. The anticipated enrollment number is 468 subjects (or 234 for intervention group and 234 for control).
2. The PHQ-9 is widely used, has good internal consistency, is well validated, and is commonly used to inquire about the degree to which an individual has experienced depressed mood over the past two weeks. Our power calculations based on our preliminary work hold the following assumptions: 1) attrition rate of 30% 2) 80% power

3) a two-sided alternative for group differences at the 0.05 level of significance for a change in PHQ-9 scores (average of 4 points, variance of 5.5).

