**Table 2: Aims, Hypotheses, and Associated Measures**

*Pre-bereavement measures collected at baseline, 14, 30, 90, and 150 days (follow-up data collection post 150 days will occur every 6 weeks until participant transitions to bereavement). Post-death measures collected at transition, 14, 30, 90, 150 and 180 days. During study wind down, participants will complete their final data collection measure based on where they are at in the intervention (e.g., if a participant is on day 90 of 150, they will complete day 90 survey as their final measure).*

Specific Aim	Hypotheses (H) and Research Questions (RQ)	Instruments and Variables	Description
Aim 1: Determine the efficacy of the Caregiver Speaks intervention in reducing depression and anxiety among hospice family caregivers of PLWD.	RQ1: What is the effect of the Caregiver Speaks intervention on caregivers' depression, anxiety (outcomes of interest)? H1a: Family caregivers receiving the intervention will	Primary Outcome: Depression Patient Health Questionnaire (PHQ-9) Secondary Outcome: Anxiety Generalized	PHQ-9: a 9-item screening tool and severity measure for depressive mood.  Internal Consistency: .87 

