### **Data Analysis Plan:**

**Statistical Assumptions.** We will examine linearity and homoskedasticity by calculating and plotting residuals and Cook's distance for all models. Where data are missing, we will use the Last Observation Carried Forward (LOCF) missing data imputation technique, given that < 30% of data were missing for any particular subject in our prior work. If the proportion of missing data is higher, we will use regression based multiple imputation. Little's MCAR test (missing completely at random) will be used to test that missingness is in no way related to the intervention. Because the sample size is relatively large, we expect that known and unknown confounders will be distributed evenly among the two randomized groups. Additional confounders will only be introduced as covariates if we find evidence of imbalance between groups at baseline. We acknowledge that this study is not powered to detect small interaction effects.

We will test whether randomization created balanced groups by comparing baseline measures and demographic characteristics, using chi-square or t-test analysis for categorical or continuous variables, respectively. Variables that differ significantly between groups will be included in regression models as potential confounders. We will include time from study enrollment to the last observation as a covariate, as well as hospice agency. We will report estimates with 95% confidence intervals. To draw inferences from our study for the likely benefit to an equivalent population, where the intervention under trial is a model of service delivery, all analyses of outcomes will be by intention-to-treat. The intention-to-treat analysis, consistent with the objectives of a pragmatic trial, will minimize the influence of "informative missingness" of the data and preserve groups' comparability.

**Statistical Analysis.** H1a: Family caregivers receiving the intervention will report lower levels of depression and anxiety (outcomes of interest), which is facilitated by higher social support (mediating variable) than those in the control group during active caregiving.

H1b: Family caregivers receiving the intervention will report lower levels of depression and anxiety (outcomes of interest), which is facilitated by higher social support (mediating variable) than those in the control group during bereavement.

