# **Caregiver Speaks Data Analysis Plan**

**January 5, 2019**

**NCT04103580**

## Data Analysis

### Statistical Assumptions

We will routinely test assumptions of linearity, independence and homoskedasticity by calculating and plotting residuals and Cook's distance for all models. Where data are missing, we will substitute the mode for categorical data and the median for continuous data, given that <0.5% of data were missing for any measure in our preliminary trial. If the proportion of missing data is higher, we will use multiple imputation. In the analysis for H1a, we will use the final measure provided by caregiver before patient death, and for H1b we will use the final measure during bereavement. Because the sample size is relatively large, we expect that known and unknown confounders will be distributed evenly among the two groups. We acknowledge that this study is not powered to detect small interaction effects. Additional confounders will only be introduced as covariates if we find evidence of imbalance between groups at baseline.

We will test whether randomization created balanced groups by comparing baseline measures and demographic characteristics, using chi-square or t-test analysis for categorical or continuous variables, respectively. Variables that differ significantly between groups will be included in regression models as potential confounders. To compare outcomes for our hypotheses, we will use the last available measure post-baseline and prior to death or the end of the study and last measure during bereavement. This is a last-observation analysis.

Carpenter and Kenward argue that, in such analyses, time to this event should be taken into account. Therefore, we will include time from study enrollment to the last observation as a covariate. We will report estimates with 95% confidence intervals. To draw inferences from our study to the likely benefit to an equivalent population where the intervention under trial is a model of service delivery, all analyses of outcomes will be by intention-to-treat. The intention-to-treat analysis, consistent with the objectives of a pragmatic trial, will minimize the influence of "informative missingness" of the data and preserve groups' comparability.

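### The missing-data rule has no limit at the patient's death and no status for visits not due, so the H1b and H2 bereavement data can be filled with scores that do not belong there

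*Protocol*

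**What the plan says.** - **Wind-down.** The note to protocol Table 2 says: "During study wind down, participants will complete their final data collection measure based on where they are at in the intervention". Its example is a caregiver on day 90 of 150 whose day-90 survey becomes the last. Protocol section IX pays everyone in full "at the completion of their final survey, regardless of whether they have entered the bereavement phase".
- **Schedule.** Table 2 fixes five pre-bereavement surveys (baseline, days 14, 30, 90, 150), then one every six weeks until transition. It fixes six post-death surveys (transition, days 14, 30, 90, 150, 180).
- **Missing data, protocol.** The Data Analysis Plan says: "Where data are missing, we will use the Last Observation Carried Forward (LOCF) missing data imputation technique". The reason given is that under 30% was missing for any one subject in earlier work. Above that, regression-based multiple imputation is used.
- **Missing data, SAP.** Statistical Assumptions substitutes the median or mode on a premise of under 0.5% missing, and otherwise uses multiple imputation.
- **Population and model.** Both documents require intention-to-treat for all outcome analyses. Both describe mixed models that accept unequal numbers of measurements.
- **Bereavement hypotheses.** The SAP says that "for H1b we will use the final measure during bereavement". H2 is worded for bereaved caregivers.
- **Sizing.** Protocol section V gives one calculation, for PHQ-9 change: 468 caregivers, 234 per arm, with "1) attrition rate of 30% 2) 80% power".

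**The concern.** H1b tests the primary outcome, PHQ-9, and the secondary outcome GAD-7 in bereavement. H2 tests grief intensity. All need a score taken after the death. The plan foresees caregivers who have no such score, and others whose bereavement follow-up is cut short for administrative reasons. Neither document says how either group enters H1b or H2.

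The imputation rules are written as if every empty cell were a missed survey. Three things can follow if they are applied as they stand:

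1. A caregiver who misses the transition survey is given a pre-death PHQ-9 or GAD-7 score as the first bereavement value.
2. A caregiver stopped early in bereavement has the last score, including the grief score (TRIG), repeated to day 180.
3. Multiple imputation invents bereavement scores for a caregiver whose relative is alive.

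The planned comparison is of slopes over time, and each of these alters slopes. The choice of who counts in H1b and H2 would also be open until the data have been seen.

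**Working it through.** **1. Which rule applies to whom.** Fixed surveys in Table 2: 5 before death + 6 after = 11. The protocol does not say whether its 30% premise is judged over all surveys, within a phase, or across the trial, so two denominators are shown.

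| Caregiver | Empty surveys | Of 11 | Of 6 post-death |
|---|---|---|---|
| Misses transition survey only | 1 | 9% | 17% |
| Stopped at bereavement day 90 | 2 | 18% | 33% |
| Stopped at bereavement day 30 | 3 | 27% | 50% |
| Never bereaved | 6 | 55% | 100% |

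Over all 11 surveys the first three rows fall under 30%, so LOCF applies. Within the bereavement phase only the first row does. The denominator also moves with the time of death: if death comes between days 30 and 90, only 3 + 6 = 9 surveys exist, and a stop at day 30 leaves 3/9 = 33% empty. The same stop can therefore trigger LOCF or multiple imputation. The never-bereaved caregiver exceeds 30% on either count, so the written rule for that caregiver is multiple imputation, if the cells count as missing at all.

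**2. What carrying forward does to a slope.** This is an illustration. Assumptions: transition is day 0, the true course is linear with slope b, and an ordinary least-squares line is fitted to the six bereavement times.

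- Times 0, 14, 30, 90, 150, 180: mean 464/6 = 77.33; Sxx = 64,096 − 464²/6 = 28,213.
- Stopped at day 30, values b × (0, 14, 30, 30, 30, 30): Sxy = b × (13,696 − 464 × 134/6) = 3,333b. Fitted slope = 3,333b/28,213 = 0.12b.
- Stopped at day 90, values b × (0, 14, 30, 90, 90, 90): Sxy = b × (38,896 − 464 × 314/6) = 14,613b. Fitted slope = 14,613b/28,213 = 0.52b.
- A pre-death score put in at transition: each point of error there moves the fitted 180-day change by 180 × 77.33/28,213 = 0.49 points in the opposite direction.

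With every caregiver filled to the same six times, the arm slope is the average of the individual slopes. If a share p of an arm is stopped at day 30, the arm slope becomes b × (1 − 0.88p). The documents do not give p. At an assumed p of 10%, 20% or 30% the factor is 0.91, 0.82 or 0.74; for stops at day 90 it is 0.95, 0.90 or 0.86. If the true course is flat after the stop, carrying forward does less harm.

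**3. Does the model resolve it?** The protocol's model has one linear time slope per arm and no term for death or phase, so it does not say which scores answer H1a and which H1b. It does accept unequal follow-up, so filling is not needed. The SAP displays a regression on the last post-baseline measure, which needs one value per caregiver, and gives no rule for H1b when no bereavement value exists.

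**4. Power.** Inputs from section V: 4 points, variance 5.5, two-sided 0.05, 80% power, 30% attrition. n per arm = 2 × (1.960 + 0.842)² × variance / 4².

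- Variance 5.5: 2 × 7.849 × 5.5/16 = 5.4, so 6 per arm; 6/0.70 gives 9, total 18.
- If 5.5 was meant as a standard deviation: 2 × 7.849 × 30.25/16 = 29.7, so 30 per arm; 30/0.70 gives 43, total 86.

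Neither gives 468. Section V names no phase, no expected number of bereaved caregivers and no grief outcome.

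**The case against.** The documents go some way towards the right answer. The SAP ties H1b to a measure taken in bereavement, H2 is worded for the bereaved, and mixed models need no filled values. No sentence instructs anyone to impute bereavement scores for a caregiver who is not bereaved. A sensible analyst might do the right thing unprompted. That stands, and it limits the point to a gap in the rules.

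It does not close the gap. The protocol's LOCF sentence is general, is not confined to analyses other than the mixed model, and has no exception at death or at the cut-off.

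Two stronger readings are tempting and are not supported:

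- *LOCF or the median would give every never-bereaved caregiver a pre-death value.* Such a caregiver lacks 6 of 11 fixed surveys, so the written fallback is multiple imputation. A median taken within the bereavement data would be a bereavement value. TRIG is a scale for bereaved people and has no pre-death value to carry.
- *The stated 80% power fails for the bereavement comparisons.* This cannot be shown. The share bereaved by wind-down is not given, and the 30% attrition is not defined by cause, so it may or may not include caregivers never bereaved. On the printed inputs, power at 234 × 0.70 = 163.8 per arm is above 99.9%. Taking 5.5 as a standard deviation, it would drop below 80% only if fewer than about 30/163.8 = 18% of retained caregivers were bereaved. Those inputs do not reproduce 468, so they cannot vouch for H1b either.

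**Conclusion.** The point holds as a defect in the rules. The missing-data rule has no limit at the patient's death and no category for visits not due, while the wind-down rule creates such visits. It can therefore distort the H1b and H2 slopes, and it leaves the intention-to-treat population for those hypotheses undefined.

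The size for one caregiver is large under the linear illustration: 12% or 52% of the true slope retained after a stop at day 30 or 90. The effect on the trial depends on how many caregivers are affected in each arm, which the documents do not give. Equal shares with the same stopping pattern would shrink the difference between arm slopes; unequal shares could bias it either way.

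On power, the conclusion is limited: 80% is not established for H1b, and none is stated for H2. A null result in bereavement should not be presented as adequately powered on the strength of section V.

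**What to change.** In the protocol's Data Analysis Plan and the SAP's Statistical Assumptions, state that:

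1. H1b and H2 are analysed in all randomised caregivers, in their assigned arm, whose patient died before the wind-down cut-off.
2. Bereavement visits of caregivers not bereaved at the cut-off, and any visit dated after the cut-off, are administratively not due. They are not filled by LOCF, median substitution or multiple imputation, and do not count towards the missing-data threshold.
3. No pre-death score is carried across the death; the planned mixed model uses the bereavement scores as observed.
4. The number not bereaved at the cut-off is reported by arm.

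If section V is revised, it should name the phase its power statement covers and the number of bereaved caregivers expected.

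The cost is wording in two documents, with no new participants or data. The downside is a bereavement analysis set smaller than all randomised, which is why the counts by arm need to be reported.
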